7.1 General Considerations and Overall Design

Prior to performing any analyses, the data will be 1) screened for entry errors; 2) checked for outliers; 3) assessed for patterns of missing data.

7.2 Population for Analysis

The following populations will be used in the analyses:

- Intent-to-treat (ITT): All subjects who received at least one intake of IP. Subjects will be analyzed according to their assigned treatment.

- Per protocol (PP): All subjects in the ITT population who were free from major protocol violations that could lead to bias
- Safety: All subjects who received at least one intake of IP. Subjects will be analyzed according to the treatment they actually received.

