7.3 Analysis for Primary Outcome

We will tabulate responses to determine frequency of difficulty understanding IP schedule, difficulty adhering to dosing schedule, difficulty using the REDCap interface, satisfaction with online study procedures, satisfaction with study staff interactions and availability, satisfaction with the frequency and volume of data collection, and difficulty with completing surveys. We will review comments from participants to identify barriers and facilitators to optimize the full-scale TLC trial.

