7.4 Analysis for Secondary Outcomes

7.4.1 Attrition

Attrition will be tabulated as the proportion of subjects who complete at minimum 70% of surveys at 12 weeks, the proportion of subjects who complete at minimum 70% of doses through 12 weeks, the proportion of subjects Lost to Follow Up (LTFU), and the % subjects that voluntarily terminate participation.

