7.5 Subject Disposition

The disposition of all subjects in the various populations will be summarized by treatment arm as follows:

- Number of subjects randomized
- Number of subjects who completed the study
- Number of subjects who discontinued IP
- Number of subjects who withdrew from the study
- Number of subjects lost to follow-up

All subjects who discontinued the study will be listed by treatment arm with the reason for discontinuation, if available

8. Data and/or Specimen Banking

Data will be shared among members of the study team with appropriate access based on study role, training, and delegation of authority. Data will be made available to assigned study monitors, the appropriate oversight authorities, the Food and Drug Administration, and other state and federal regulatory authorities as required by state and federal law.

De-identified data may be shared for future research. Requests will be evaluated on a case-by-case basis by PI. No data will be released without proof of IRB approval or determination. Agreements as required by local policies will be completed when necessary, including data use agreements and material transfer agreements.

The study will be registered with one or more recognized clinical study registries, e.g., www.clinicaltrials.gov.

All data and results and all intellectual property rights in the data and results derived from the study will be the property of the Sponsor who may utilize them in various ways, such as for submission to regulatory authorities or shared with research institutions, as needed.

The final Clinical Study Report will be submitted to the ethics committee and regulatory authorities, if required.

The Sponsor encourages the communication and/or publication of the results by the consortium of partners in accordance with the terms of the Clinical Trial Agreement.

Subjects will have the option of consenting to be contacted for future related studies. If subjects choose this option, their name and contact information will be stored in a password-protected file stored on a secure, Emory server.

9. Sharing of Results with Participants

Individual subject results will not be shared with participants. Participants interested in knowing their randomization assignment may request that staff release that information after unblinding occurs after database lock. Participants desiring study results may request that staff provide them links to any publications resulting from the trial.

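### The set called ITT in section 7.2 contains only dosed subjects, so a subject randomised but never dosed is in no analysis population, and no attrition proportion in 7.4.1 is tied to all randomised

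*Combined protocol and SAP*

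**What the plan says.** Section 7.2 introduces three sets with the words "The following populations will be used in the analyses". They are:

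- "Intent-to-treat (ITT): All subjects who received at least one intake of IP", analysed by assigned arm;
- "Per protocol (PP): All subjects in the ITT population who were free from major protocol violations that could lead to bias", which makes this set a subset of the first one;
- "Safety: All subjects who received at least one intake of IP", analysed by treatment received.

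Section 7.4.1 lists four proportions: 70% survey completion, 70% dose completion, loss to follow-up and voluntary termination. Two of them read "the proportion of subjects who complete at minimum 70% of doses through 12 weeks, the proportion of subjects Lost to Follow Up (LTFU". All four refer only to subjects, and none cites a 7.2 set or a denominator. The section 4 endpoints are worded the same way.

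Section 7.3 handles the primary outcome by tabulating the end-of-study survey: "We will tabulate responses to determine frequency of difficulty understanding IP schedule". It does not say out of how many.

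Section 7.5 (Subject Disposition) plans, by arm, the "Number of subjects randomized" along with counts of completion, discontinuation, withdrawal and loss. It adds that "All subjects who discontinued the study will be listed by treatment arm with the reason for discontinuation, if available".

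**The concern.** Intention to treat normally means everyone randomised, and a reader of the report will assume so. Here the label belongs to a set defined by having taken the product.

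The excluded subject matters in this design. Randomisation takes place at the Day 0 televisit (6.5.2). The product then goes out by courier or overnight mail (5.8) and is first taken on Day 1 (6.5.3). Losing someone between those two points, through a change of mind or a failed delivery, is a failure of the decentralised process itself. Such a subject is not a screen failure, because 16.4 stops at randomisation. Section 14 does not replace the subject if the exit counts as drop-out, withdrawal or loss to follow-up.

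If the 7.2 sets are followed, these failures leave the adherence and attrition rates. If they are not followed, the denominator is undefined, and two analysts could report different rates from the same data.

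**Working it through.** **Set logic.** ITT and Safety have the same members and differ only in assigned versus received arm. Per protocol is a subset of ITT. The union of the three is therefore the dosed subjects, and a randomised, never-dosed subject is in none. Of the four proportions in 7.4.1, 0 state a denominator.

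**Inputs from the documents**
- Supply: 28 + 56 = 84 days (5.8).
- Capsules per day: 1 + 2 = 3 (5.8), so 84 × 3 = 252 capsules, and 70% of 252 is 176.4. A never-dosed subject has 0/252 and always fails the dose criterion.
- Sample size: 24 needed to complete and about 36 enrolled and screened (section 14); up to 36 (section 1). No screen-failure or drop-out rate is given, so 36 cannot be re-derived. It only implies a combined loss of 1 − 24/36 = 33.3%.

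**Assumptions.** The number randomised, N, is not stated. I use 24 and 36 as the range; 36 is a ceiling, because section 14 counts screen failures in it. The number never dosed, k, and all event counts are illustrative.

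**Dose completion.** Let x subjects meet the criterion and p = x/N. All k never-dosed subjects fail, so

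x/(N − k) − x/N = p·k/(N − k),

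which is positive whenever x > 0 and k > 0, and zero when k = 0. Intervals are 95% Clopper-Pearson.

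| N | k | All randomised | Dosed only | Excess |
|---|---|---|---|---|
| 24 | 0 | 18/24 = 75.0% (53.3–90.2) | the same | 0 |
| 24 | 1 | 75.0% | 18/23 = 78.3% (56.3–92.5) | 0.75 × 1/23 = 3.3 points |
| 24 | 2 | 75.0% | 18/22 = 81.8% (59.7–94.8) | 0.75 × 2/22 = 6.8 points |
| 36 | 1 | 27/36 = 75.0% (57.8–87.9) | 27/35 = 77.1% (59.9–89.6) | 0.75 × 1/35 = 2.1 points |
| 36 | 2 | 75.0% | 27/34 = 79.4% (62.1–91.3) | 0.75 × 2/34 = 4.4 points |

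**Loss to follow-up and surveys.** Here a never-dosed subject may or may not count as an event. If m of the k do, the dosed-only rate is (x − m)/(N − k), which is below x/N when m/k exceeds x/N and above it when m/k is smaller. With N = 24 and k = 2:

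- Loss to follow-up, 4 lost: 4/24 = 16.7% (4.7–37.4) becomes 2/22 = 9.1% (1.1–29.2) if both never-dosed subjects were among the lost, or 4/22 = 18.2% (5.2–40.3) if neither was.
- Surveys, 20 meeting 70%: 20/24 = 83.3% (62.6–95.3) becomes 20/22 = 90.9% (70.8–98.9) if neither never-dosed subject met it, or 18/22 = 81.8% (59.7–94.8) if both did. The second case is possible because 16.1 asks subjects who stop the product to continue assessments.

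**The case against.** The strongest reply is that 7.4.1 does not instruct anyone to use a dosed-only denominator. It names no set, and section 20.4 says that data collected before loss or withdrawal will be analysed, which leans towards inclusion. The disposition table already reports the number randomised, and exits are listed with reasons. Loss to follow-up over all randomised can be read from it. The dose rate can be recalculated by hand, because a never-dosed subject cannot be in the numerator. The route is also narrow: windows run from Day 1 and a Day 1 contact is required (6.7, notes a and h), so a late parcel alone need not leave anyone undosed. The documents give no never-dosed rate, and it may be zero. A dosed set analysed as assigned is a familiar choice under the name modified ITT.

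Much of this stands. Exclusion is an inference from 7.2, the subjects are not hidden, and the counts are assumed. The value of 24 is also ambiguous: it may be the number of completers rather than the number randomised. But 20.4 concerns which data are kept and sets no denominator. The disposition table does not recover survey completion, or separate voluntary termination from other withdrawals. Its lead-in also refers back to the analysis populations, which are the dosed-only sets.

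**Conclusion.** The concern holds. No analysis set in 7.2 contains a randomised subject who never takes the product, and no proportion in 7.4.1 is tied to all randomised.

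If the 7.2 sets are applied and at least one such subject exists, 70%-of-doses is overstated. Survey completion probably is too. Loss to follow-up or voluntary termination is understated when the never-dosed subjects left that way, and slightly overstated when they did not.

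Under the assumed counts, one or two never-dosed subjects move dose completion by about 2 to 7 points, inside 95% intervals about 30 to 37 points wide (87.9 − 57.8 = 30.1; 90.2 − 53.3 = 36.9). The documents state no go/no-go threshold, so the cost is to the accuracy of the reported feasibility rates and not to a pre-specified decision. It should be fixed because those rates are meant to inform a larger trial and the correction is nearly free.

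**What to change.** - **7.2:** define ITT as all randomised subjects, analysed by assigned arm. Alternatively, rename the present set modified ITT and add an all-randomised set. Keep the at-least-one-intake rule for Safety.
- **7.4.1:** state all randomised as the denominator for each of the four proportions.
- **7.3:** give the number of end-of-study surveys returned over the number randomised, beside the tabulated responses. Section 6.5.7 also asks for the survey at early termination, so this count shows how far that worked.
- **7.4.2, only if ITT is redefined:** this section currently refers to ITT for adverse events. Keep those tables in the dosed Safety set, by assigned arm and by treatment received, because adverse events are collected only after the first dose (6.7, note c).

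The cost is a few words in four sections. No new data are needed: the number randomised and the Day 1 contact are already planned. Some reported percentages may be slightly less favourable.

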7.3 Analysis for Primary Outcome

We will tabulate responses to determine frequency of difficulty understanding IP schedule, difficulty adhering to dosing schedule, difficulty using the REDCap interface, satisfaction with online study procedures, satisfaction with study staff interactions and availability, satisfaction with the frequency and volume of data collection, and difficulty with completing surveys. We will review comments from participants to identify barriers and facilitators to optimize the full-scale TLC trial.

7.4 Analysis for Secondary Outcomes

7.4.1 Attrition

Attrition will be tabulated as the proportion of subjects who complete at minimum 70% of surveys at 12 weeks, the proportion of subjects who complete at minimum 70% of doses through 12 weeks, the proportion of subjects Lost to Follow Up (LTFU), and the % subjects that voluntarily terminate participation.

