A host of medications have been investigated in the treatment of acute COVID-19, though few drugs have been studied in formal randomized controlled trials in the post-acute phase to address persistent symptoms and long-term sequelae. A panel assembled by the CURE Drug Repurposing Collaboratory (CDRC) – a public-private partnership - that includes at least one of each of the following—physician, pharmaceutical engineer, pharmacist, public health professional, immunologist, patient, and drug repurposing expert—reviewed the available data for over 60 candidate therapeutic approaches. Several drugs appeared to be promising based on early anecdotal reports and plausible mechanisms. Given the urgency of finding answers and the need for randomized controlled trials to begin to determine drugs that are effective for PASC, the panel selected the following treatment as an initial approach.

As mast cell activation syndrome is one theorized mechanism of severe acute COVID-19 and a proposed physiologic derangement contributing to PASC, histamine receptor antagonists (HRA), such as famotidine and cetirizine, have garnered interest as possible drug candidates. (See section 5.1.2). These agents may modulate their effects through reductions in cellular inflammatory mediators, such as histamine, serotonin, TGFb, VEGF, IL6, IL8,

interferons, and NETs and modulation of dysregulated T cells. Administration of HRAs in a relatively small cohort of PASC patients (N=25) demonstrated a 72% improvement in patient reported symptoms, of which, 20% had complete symptom resolution [34]. This is compared with those who received no treatment (N=40) who experienced a 50% improvement, with complete resolution in 4% in the same period.

4. Study Endpoints

Primary endpoint:

- Subject reported (patient reported outcome [PRO]) end of study questionnaire

Secondary endpoints:

- % subjects who complete 70% of PRO surveys/questionnaires at 12 weeks
- % subjects who complete 70% of IP doses through 12 weeks
- % subjects Lost to Follow Up (LTFU)
- % subjects voluntarily terminate participation
- Incidence of adverse events and serious adverse events
- Number of discontinuations or temporary suspensions of IP

5. Study Intervention/Investigational Agent

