5.8 Provision of Investigational Product to Participants

Following receipt of confirmed subject eligibility and consent, IDS will randomize subjects as described below in Section 6.1. IDS will prepare the courier or overnight mail service, which will deliver IP to participants according to the below dosing schedule.

Clear instructions will be provided to the subject regarding the number and type of capsules to be ingested at each IP administration time point listed.

DOSING SCHEDULE

Antihistamine and Placebo Arm Dosing^{1,2}

Day 0-Day 84:

Cetirizine 10 mg or placebo (1 capsule) QD
Famotidine 20mg or placebo (1 capsule) BID

1. Dose to be assessed at Day 14. Subjects unable to tolerate will be withdrawn from study
2. Subjects receive initial shipment of 28 days' supply at Day 0, and shipment of remaining 56 days' supply after Day 14 assessment

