6.1 Study Design

This is a fully decentralized, single center, randomized, double-blind, placebo controlled, clinical trial to evaluate the safety, tolerability, and feasibility of a potential treatment for PASC.

Upon confirmation of eligibility, the investigational pharmacist will randomize subjects 2:1 treatment versus placebo. Treatment consists of 10mg of cetirizine daily and 20mg of famotidine twice daily. Placebos will match the morphology of the treatments but contain no active ingredients. Study subject and study team will be blind to assigned treatment; only the IDS will be unblind.

Subjects will be followed for safety, tolerability, and responses to patient reported outcome (PROs) over 12 weeks. At Week 12, End of Study, subjects will be required to complete a questionnaire that addresses several aspects of feasibility of participating in the study.

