6.5.2 Randomization/Day 0 will be a televisit with the study physician for a baseline evaluation to confirm eligibility. Study clinician will confirm adequate hepatic and renal function after onset of Long COVID symptoms through review of participant's labwork in historical medical records. Study clinician will confirm negative pregnancy status in participants capable of becoming pregnant via urine or serum β -HCG within 30 days of randomization/Day 0. Women of childbearing potential who don't anticipate a pregnancy test at a clinician's office within 30 days of randomization will be mailed a urine pregnancy test kit by study staff. Subjects will take the pregnancy test during the Randomization/Day 0 televisit and show the result to the study physician. If additional physical exam is needed per study physician discretion, the study physician will conduct a telemedicine exam of the following systems: Constitution, Head, eyes, ears, nose and throat, Cardiovascular, Respiratory, Gastrointestinal, Genitourinary (CVA tenderness per subject exam), Musculoskeletal, Skin, Neurological, Psychological. Subjects will be asked to report their most burdensome PASC symptom at Day 0.

Upon confirmation of eligibility, subjects will be randomized as described in Section 6.1 and shown in Section 6.2.

6.5.3 Day 1: Participant receives IP and self-administers.

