6.5.4 Days 2-84: Participant takes IP daily

6.5.5 Weekly: Participant completes adverse event log, study medication adherence log, concomitant medication log, self-reported persistent symptoms questionnaire

6.5.6 Days 42, 63, and 84, all +/- 3 days, subjects enter patient reported outcome (PRO) data into REDCap.

- PRO data to be collected
 - WHODAS 2.0 36-item score
 - PROMIS Fatigue 7a
 - Insomnia Severity Index
 - PROMIS Cognitive Function Short Form 6A
 - DSQ-PEM Short Form
 - Headache Diary (completed daily during the 7 days prior to visit)
 - COMPASS 31

6.5.7 Day 84/End of Study (EOS) or Early Termination: Participants complete End of Study survey

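### Does the 70% adherence endpoint need a defined dose unit and a split by product?

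*Combined protocol and SAP*

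**What the plan says.** Section 4 lists, as a secondary endpoint, the percentage of "subjects who complete 70% of IP doses through 12 weeks". Section 7.4.1 repeats it as "the proportion of subjects who complete at minimum 70% of doses through 12 weeks", next to survey completion, loss to follow-up and voluntary termination. Neither section defines a dose, and neither asks for a table by product.

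The regimen has two products: "Treatment consists of 10mg of cetirizine daily and 20mg of famotidine twice daily". Section 5.8 tells subjects "the number and type of capsules to be ingested at each IP administration time point listed", and its schedule gives one capsule per administration for each product. Section 5.11 takes adherence from a weekly self-reported log, with a coordinator's pill count at study visits as a supplement. The log form is not in the documents.

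The dosing period is stated in two ways. The schedule heading in Section 5.8 runs from Day 0 to Day 84. Section 6.5 has "Day 1: Participant receives IP and self-administers" and then "Days 2-84: Participant takes IP daily", and the Schedule of Events in Section 6.7 also starts dosing on Day 1. A footnote to Section 5.8 ships 28 days' "supply at Day 0, and shipment of remaining 56 days", which is 84 days in all.

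**The concern.** Adherence is a named secondary objective, and the pilot exists to inform a larger trial. If a dose means a capsule, famotidine supplies two thirds of the count, so a subject can pass while leaving out much of the cetirizine. If a dose means a day on which the whole regimen was taken, the same subject fails. A unit chosen after the data are seen could therefore change the reported rate, and a high pooled rate would not by itself show that both products were taken.

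Selective omission is conceivable. Section 17.1 lists somnolence and fatigue among the common side effects of cetirizine, and many subjects are enrolled for fatigue. Pill counts might not reveal it, because footnote h of Section 6.7 requires staff contact only up to Day 14 and as needed after that.

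**Working it through.** The plan states no adherence figure to reproduce, so the check is direct counting. Inputs: one cetirizine and two famotidine capsules a day (Sections 5.8 and 6.1), the 70% cut (Sections 4 and 7.4.1), and 84 days, with 85 as the alternative.

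**Pass mark by capsule, 84 days.** 84 + 168 = 252 capsules; 0.70 × 252 = 176.4, so 177.

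**Example subject: cetirizine 42/84 (50%), famotidine 151/168 (90%).**

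| Unit | Count | Result |
|---|---|---|
| Capsule | (42 + 151)/252 = 193/252 = 76.6% | passes |
| Each product separately | cetirizine 50.0% | fails |
| Full-regimen day | at most 42/84 = 50.0% | fails |
| Two time points a day, all capsules due required | 109/168 to 126/168 = 64.9% to 75.0%; mark 0.70 × 168 = 117.6, so 118 | either |

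The last row assumes that cetirizine is taken with the evening famotidine. If all 17 missed famotidine capsules are morning ones, the count is (84 − 17) + 42 = 109. If they all fall on evenings when cetirizine was also missed, it is 84 + 42 = 126.

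**How far the pooled count can stretch.** With famotidine at 151, 177 − 151 = 26 cetirizine capsules (31.0%) are enough. With full cetirizine, 177 − 84 = 93 famotidine capsules (55.4%) are enough.

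**85 days.** 3 × 85 = 255; 0.70 × 255 = 178.5, so 179. Famotidine 153/170 with cetirizine 42/85 gives 195/255 = 76.5%, again a pass. The one-day discrepancy changes nothing here.

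**When pooled and per-product rates agree.** If a subject takes each product at the same rate p, the pooled rate is (84p + 168p)/252 = p. The pooled and per-product classifications then agree, apart from rounding to whole capsules. They part only when the products are taken unequally.

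**Weight of one subject.** 1/24 = 4.2 points with the 24 subjects that Section 14 needs to complete; 1/36 = 2.8 points at the cap of 36 in Section 1. For scale, assume that between 70% and 90% of 24 subjects reach the mark. The approximate 95% half-width is 1.96 × √(0.7 × 0.3/24) = 18 points at 70% and 1.96 × √(0.9 × 0.1/24) = 12 points at 90%. One reclassified subject is small against either.

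**The case for a change.** The strongest case for a change is that it would be cheap. Stating the unit and adding two rows to a table costs little, and adherence is a result the larger trial will use. The Day 14 assessment ("Subjects unable to tolerate will be withdrawn from study") and the counts of discontinuations and suspensions do not reveal intermittent under-use of one product. Of the 252 capsules, (84 − 14) × 3 = 210 (83%) fall due after the last contact that footnote h requires.

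Part of this stands. The definition is unwritten, the arithmetic is right, and a report that gives the rate should name its unit. Section 5.11, which ties pill counts to study visits, and footnote h do not fit together neatly. However, Section 7.5.1 calls Weeks 6, 9 and 12 study visits, and the weekly log is the main source in any case.

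The rest is weaker. The full-regimen-day reading strains the wording: each administration is one capsule, so doses and capsules give the same count. Unequal use remains a possibility with no data behind it. The log may already record each product. Section 7.3 tabulates difficulty with the dosing schedule, and reviews comments on barriers, as part of the primary outcome, which is where trouble with one product would be likely to surface.

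Unlogged weeks also raise a question: full intake with 8 of 12 logs is 66.7% if unlogged means not taken, and 100% on logged weeks. But scoring silence as non-adherence would mix two things that Section 4 keeps apart, survey completion and dose completion. Sections 6.6 and 20.4 already have staff pursue overdue entries.

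**Conclusion.** No change to the plan follows. This is an unwritten detail that an analyst would fill sensibly, by counting scheduled capsules, naming that unit in the report and, where the log allows, showing the two products side by side. The pooled rate obtained that way is sound for what the plan asks of it, a descriptive feasibility figure with no test, sample size or progression rule attached.

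The unit alters a subject's classification only in particular patterns of missed capsules, such as the constructed 50%/90% case. Each such subject moves the rate by 4.2 points with 24 subjects or 2.8 with 36. How many there would be cannot be estimated from the documents.

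The Day 0 and Day 1 statements of the dosing period contradict each other by one day and must be reconciled. This is a clerical matter and leaves the result above unchanged. The conclusion rests on the endpoint staying descriptive; it would need another look if a progression threshold were ever attached to it.
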